12.1 Overview

This section defines the types of safety data that will be collected under this protocol and outlines the procedures for appropriately collecting, grading, recording, and reporting those data. AEs that are classified as serious according to the definition of health authorities must be reported promptly (per [Section 12.5](#)) to the sponsor DAIT/NIAID. Appropriate notifications will also be made to site PIs, IRB, and health authorities.

Information in this section complies with *International Conference on Harmonisation (ICH) Guideline E2A: Clinical Safety Data Management: Definitions and Standards for Expedited Reporting*, *ICH Guideline E-6: Guideline for Good Clinical Practice (GCP)*, 21CFR Parts 312 and 320, and applies the standards set forth in the National Cancer Institute (NCI), Common Terminology Criteria for Adverse Events (CTCAE), Version 5.0: <http://ctep.cancer.gov/reporting/ctc.html>.

12.2 Definitions

12.2.1 Adverse Event (AE)

Any untoward or unfavorable medical occurrence associated with the subject's participation in the research, whether or not considered related to the subject's participation in the research (modified from the definition of adverse events in 21 CFR 312.32(a), the International Council for Harmonisation of Technical Requirements for Pharmaceuticals for Human Use (ICH) E-6(R2) Guidelines for Good Clinical Practice and OHRP "Guidance on Reviewing and Reporting Unanticipated Problems Involving Risks to Subjects or Others and Adverse Events (1/15/07)" <http://www.hhs.gov/ohrp/policy/advevntguid.html#Q2>).

For this study, an AE will include any untoward or unfavorable medical occurrence associated with:

- **Study Treatment regimen:** An AE occurring from the time of consent and within one month of *S. hominis* A9 product administration
- **Study mandated procedures:**
 - **Blood Draw** (to only occur at Unscheduled Visit at the discretion of the study physician or other qualified medical professional)
The following events related to the blood draw procedure will be considered an AE if they occur within 48 hours of the blood draw:
 - Fainting / Vasovagal Events

- Bruising at the puncture site larger than 2 cm in diameter ○ Bleeding from the puncture site lasting more than 30 minutes ○ Swelling at puncture site larger than 2 cm

12.2.1.1 Suspected Adverse Reaction (SAR)

Any adverse event for which there is a reasonable possibility that the drug caused the adverse event. For the purposes of IND safety reporting, 'reasonable possibility' means there is evidence to suggest a causal relationship between the drug and the adverse event. Suspected adverse reaction implies a lesser degree of certainty about causality than adverse reaction, which means any adverse event caused by a drug (21 CFR 312.32(a)).

12.2.2 Unexpected Adverse Event or Unexpected Suspected Adverse Reaction

An adverse event or suspected adverse reaction is considered "unexpected" if it is not listed in the Investigator Brochure or is not listed at the specificity or severity that has been observed; or, if an investigator brochure is not required or available, is not consistent with the risk information described in the general investigational plan or elsewhere in the current application, as amended. For example, under this definition, hepatic necrosis would be unexpected (by virtue of greater severity) if the investigator brochure referred only to elevated hepatic enzymes or hepatitis. Similarly, cerebral thromboembolism and cerebral vasculitis would be unexpected (by virtue of greater specificity) if the investigator brochure listed only cerebral vascular accidents. "Unexpected," as used in this definition, also refers to adverse events or suspected adverse reactions that are mentioned in the investigator brochure as occurring with a class of drugs or as anticipated from the pharmacological properties of the drug, but are not specifically mentioned as occurring with the particular drug under investigation 21 CFR 312.32(a)).

12.2.3 Serious Adverse Event (SAE) or Serious Suspected Adverse Reaction

An adverse event or suspected adverse reaction is considered "serious" if, in the view of either the investigator or the Sponsor, it results in any of the following outcomes: Death, a life-threatening adverse event, inpatient hospitalization or prolongation of existing hospitalization, a persistent or significant incapacity or substantial disruption of the ability to conduct normal life functions, or a congenital anomaly/birth defect. Important medical events that may not result in death, be life-threatening, or require hospitalization may be considered serious when, based upon appropriate medical judgment, they may jeopardize the patient or subject and may require medical or surgical intervention to prevent one of the outcomes listed in this definition. Examples of such medical events include allergic bronchospasm requiring intensive treatment in an emergency room or at home, blood dyscrasias or convulsions that do not result in inpatient hospitalization, or the development of drug dependency or drug abuse (21 CFR 312.32(a)).

Elective hospitalizations are not to be reported as an SAE unless hospitalization is prolonged due to complications.

12.3 Grading and Attribution of Adverse Events

12.3.1 Grading Criteria

The study site will grade the severity of AEs experienced by the study participants according to the criteria set forth in the NCI-CTCAE Version 5.0. This document (referred to herein as the NCI-CTCAE manual) provides a common language to describe levels of severity, to analyze and interpret data, and to articulate the clinical significance of all AEs. The NCI-CTCAE has been reviewed by the study investigators and sponsor and has been deemed appropriate for the participant population to be studied in this protocol.

AEs will be graded on a scale from 1 to 5 according to the following standards in the NCI-CTCAE manual:

Grade 1 = mild AE

Grade 2 = moderate AE

Grade 3 = severe AE

Grade 4 = life-threatening AE or urgent intervention indicated

Grade 5 = death

Events grade 1 or higher will be recorded on the appropriate AE eCRF for this study.

For grading an abnormal value or result of a clinical or laboratory evaluation (including, but not limited to, a radiograph, an ultrasound, an electrocardiogram etc.), a treatment-emergent AE is defined as an increase in grade from baseline or from the last post-baseline value that doesn't meet grading criteria. Changes in grade from screening to pre-treatment and enrollment at Day 0 will also be recorded as AEs, but are not treatmentemergent. If a specific event or result from a given clinical or laboratory evaluation is not included in the NCICCTCAE manual, then an abnormal result would be considered an AE if changes in therapy or monitoring are implemented as a result of the event/result.

For additional information and a printable version of the NCI-CTCAE manual, consult the NCI-CTCAE web site: <http://ctep.cancer.gov/reporting/ctc.html>.

12.3.2 Attribution Definitions

The relationship, or attribution, of an AE to the investigational product regimen or study procedure(s) will initially be determined by the site investigator and recorded on the appropriate AE/SAE eCRF. Final determination of attribution for safety reporting will be determined by the DAIT/NIAID Medical Monitor. The relationship of an AE to study therapy regimen or procedures will be determined using the descriptors and definitions provided in Table 12.3.2.

Table 12.3.2 Attribution of Adverse Events

| Code | Descriptor | Relationship (to investigational product regimen or study procedure: blood draw) |
|---------------------------|-------------|--|
| UNRELATED CATEGORY | | |
| 1 | Not Related | The adverse event is clearly not related: there is insufficient evidence to suggest a causal relationship. |
| RELATED CATEGORIES | | |
| 2 | Possible | The adverse event has a reasonable possibility to be related; there is evidence to suggest a causal relationship. |
| 3 | Related | The adverse event is clearly related. |

12.4 Collection and Recording of Adverse Events

12.4.1 Collection Period

AEs (including SAEs) will be collected from the time of consent until a participant completes study participation or until 30 days after he/she prematurely withdraws (without withdrawing consent) or is withdrawn from the study.

12.4.2 Collecting Adverse Events

AEs (including SAEs) may be discovered through any of these methods:

- Observing the participant
- Interviewing the participant in an objective manner [e.g., using structured questioning]
- Receiving an unsolicited complaint from the participant
- Receiving a call from the participant outside of their regular study visits; Instructions for contacting the clinic will be provided on an instructional handcard at the Treatment Visit.
- In addition, an abnormal value or result from a clinical or laboratory evaluation can also indicate an AE, as defined in [Section 12.3](#).

12.4.3 Recording Adverse Events

Throughout the study, the investigator will record AEs and SAEs as described previously ([Section 12.2](#)) on the appropriate AE/SAE eCRF regardless of the relationship to study therapy regimen or study procedure.

Once recorded, an AE/SAE will be followed until it resolves with or without sequelae or until the end of study participation, or until 30 days after the participant prematurely withdraws (without withdrawing consent)/or is withdrawn from the study, whichever occurs first.

12.5 Reporting of Serious Adverse Events and Adverse Events

12.5.1 Reporting of Serious Adverse Events to DAIT/NIAID

This section describes the responsibilities of the site investigator to report SAEs to the sponsor and the SACCC via the SAE eCRF. Timely reporting of AEs is required by 21 CFR 312.32 and ICH E6 guidelines.

Site investigators will report all SAEs (see [Section 12.2.3](#)), regardless of relationship or expectedness within 24 hours of discovering the event.

For SAEs, all requested information on the SAE eCRF will be provided. However, unavailable details of the event will not delay submission of the known information. An Initial SAE eCRF shall include as much information as possible, but at a minimum will include the following:

- AE term
- Relationship to investigational product
- Relationship to stopping protocol prohibited medications/therapy
- Relationship to study procedure
- Reason why the event is serious

- Supplementary CRF pages that are current at the time of SAE reporting: medical history, concomitant medications, demographics, and investigational product administration

As additional details become available, the SAE eCRF should be updated and submitted. Every time the SAE eCRF is submitted, it should be electronically signed by the investigator or sub-investigator.

For additional information regarding SAE reporting, contact Rho Product Safety:

Rho Product Safety
[name]
[name]
Toll-free: [name]
SAE Fax Line: [name]
Email: [contact]

12.5.2 Reporting to Health Authority

After an AE, requiring 24-hour reporting (per [Section 12.5.1](#)), is submitted by the site investigator and assessed by DAIT/NIAID, there are two options for DAIT/NIAID to report the AE to the appropriate health authorities:

12.5.2.1 Annual Reporting

DAIT/NIAID will include in the IND Annual Report to the FDA all reported AEs classified as:

- Serious, expected, suspected adverse reactions (see Section [12.2.1.1](#) and [Section 12.2.2](#))
- Serious and not a suspected adverse reaction (see [Section 12.2.2](#))
- Pregnancies

Note that all AEs (not just those requiring 24-hour reporting) will be reported in the IND Annual Report.

12.5.2.2 Expedited Safety Reporting

This option, with 2 possible categories, applies if the adverse event is classified as one of the following:

Category 1: Serious and unexpected suspected adverse reaction [SUSAR] (see [Section 12.2.1.1](#), [Section 12.2](#), and 21 CFR 312.32(c) (1) i).

The sponsor shall report any suspected adverse reaction that is both serious and unexpected.

The sponsor shall report an adverse event as a suspected adverse reaction only if there is

evidence to suggest a causal relationship between the investigational product and the adverse event, such as:

1. A single occurrence of an event that is uncommon and known to be strongly associated with investigational product exposure (e.g., sepsis, cellulitis, or deep tissue infections);
2. One or more occurrences of an event that is not commonly associated with investigational product exposure, but is otherwise uncommon in the population exposed to the investigational product (e.g., tendon rupture);
3. An aggregate analysis of specific events observed in a clinical trial (such as known consequences of the underlying disease or condition under investigation or other events that commonly occur in the study population independent of investigational product regimen) that indicates those events occur more frequently in participants receiving the investigational product than in a concurrent or historical control group.

Category 2: Any findings from studies that suggests a significant human risk

The sponsor shall report any findings from other epidemiological studies, analyses of adverse events within the current study or pooled analysis across clinical studies, or animal or *in vitro* testing (e.g. mutagenicity, teratogenicity, carcinogenicity) that suggest a significant risk in humans exposed to the investigational product that would result in a safety-related change in the protocol, informed consent, investigator brochure or other aspects of the overall conduct of the study.

DAIT/NIAID shall notify the FDA and all participating investigators of expedited Safety Reports within 15 calendar days; unexpected fatal or immediately life-threatening suspected adverse reaction(s) shall be reported as soon as possible or within 7 calendar days.

12.5.3 Reporting of Adverse Events to IRB/IEC

All investigators shall report AEs, including expedited reports, in a timely fashion to their local IRB in accordance with applicable regulations and guidelines. All Safety Reports to the FDA shall be distributed by DAIT/NIAID or designee to UCSD for site IRB submission.

12.6 Pregnancy Reporting

The investigator shall be informed of any pregnancy in a female study participant immediately upon becoming aware of the event. If a female participant becomes pregnant prior to the Treatment Visit, the participant will no longer be eligible to participate in the study and will be withdrawn as described in [Section 11.2](#). If a pregnancy occurs following the Treatment Visit, the pregnant participant will continue to be followed per the Schedule of Events. The investigator shall counsel the participant and discuss the risks of continuing with the pregnancy and the possible effects on the fetus. Monitoring of the pregnant participant shall continue until the conclusion of the pregnancy.

The investigator shall report to the SACCC all pregnancies within 1 business day of becoming aware of the event using the Pregnancy eCRF. The SACCC will report all pregnancies to DAIT/NIAID using the procedures as outlined in the Safety Management Plan. All pregnancies identified during the study shall be followed to conclusion, and the outcome of each must be reported. The Pregnancy eCRF shall be updated and submitted to the SACCC

when details about the outcome are available. When possible, similar information shall be obtained for a pregnancy occurring in a partner of a study participant. Information on this pregnancy will be collected on the Pregnancy eCRF. In order for Sponsor or designee to collect any pregnancy surveillance information from the female partner, the female partner must sign an informed consent form for disclosure of this information.

Information requested about the delivery shall include:

- Gestational age at delivery ○ Birth weight, length, and head circumference ○ Gender
- Appearance, pulse, grimace, activity, and respiration (APGAR) score at 1 minute, 5 minutes, and 24 hours after birth, if available ○ Any abnormalities.

Should pregnancy complications result in a congenital abnormality, birth defect, miscarriage, or medically indicated abortion - an SAE shall be submitted to the SACCC using the SAE reporting procedures described above.

12.7 Reporting of Other Safety Information

An investigator shall promptly notify their local IRB, in accordance with applicable regulations and guidelines, as well as the SACCC and DAIT/NIAID via email when an “unanticipated problem involving risks to participants or others” is identified, which is not otherwise reportable as an adverse event.

12.8 Review of Safety Information

12.8.1 Medical Monitor Review

The DAIT/NIAID Medical Monitor shall receive monthly reports from the SACCC compiling new and accumulating information on AEs, SAEs, and pregnancies recorded by the study site on appropriate eCRFs.

In addition, the DAIT/NIAID Medical Monitor shall review and make decisions on the disposition of the SAE and pregnancy reports received by the SACCC (See Sections [12.5.1](#) and [12.6](#)).

12.8.2 DSMB Review

The SACCC will provide the NIAID Allergy-Asthma [Alpha] DSMB with a listing of all AEs and SAEs at least annually. Furthermore, the DSMB will be informed of expedited reports of SAEs.

12.8.2.1 Planned DSMB Reviews

The DSMB shall review safety data at least yearly during planned DSMB Data Review Meetings. Data for the planned safety reviews will include, at a minimum, a listing of all reported AEs and SAEs.

12.8.2.2 *Ad hoc* DSMB Reviews

In addition to the pre-scheduled data reviews and planned safety monitoring, the DSMB may be called upon for *ad hoc* reviews when an event occurs that is of sufficient concern to the DAIT/NIAID Medical Monitor and/or the protocol chair(s) to warrant DSMB review, this includes all Expedited Safety Reports. The DSMB will be notified within 24 to 48 hours by the NIAID Medical Monitor and will promptly review any event that potentially impacts safety at the request of the protocol chair or DAIT/NIAID or any occurrence that meets the definition of the *Study Stopping Rules* defined in [Section 11.5](#).

After review of the data, the DSMB will make recommendations regarding study conduct and/or continuation.

12.8.2.2.1 Temporary Suspension of Enrollment and Study Treatment for *ad hoc* DSMB Safety Review

A temporary halt in screening, enrollment, and investigational product application will be implemented if an *ad hoc* DSMB safety review is required. New participants will not be consented for study participation during the enrollment and treatment halt. Participants who were screened or who completed the Pre-treatment Visit but who are not yet randomized will not be allowed to continue with the Day 0 Treatment Visit. All participants not randomized within 14 days of the Screening Visit must rescreen. Follow up visits will continue per the Schedule of Events.

13. Statistical Considerations and Analytical Plan

13.1. Overview

This is a pilot, open-label, single-center trial designed to assess the survival of transplanted *S. hominis* A9 on the skin of adults with moderate-to-severe atopic dermatitis on the ventral arms who are culture positive or negative for *S. aureus* colonization.

13.2. Endpoints

13.2.1 Primary Endpoint

The primary endpoint for this pilot study is the duration of survival, measured as the time needed for the CoNS CFU to drop below baseline density measured before application of ShA9 + 100 CFU/cm² on the lesional ventral arm skin of AD participants positive for *S. aureus* (AD SA+)

13.2.2 Secondary Endpoints

1. The duration of survival, measured as the time needed for the CoNS CFU to drop below baseline density measured before application of ShA9 + 100 CFU/cm² on the non-lesional ventral arm skin of AD participants positive for *S. aureus* (AD SA+)
2. The count of serious and non-serious treatment-emergent AEs per participant during the time period of Day 0 to Day 31

13.2.3 Exploratory Endpoints

1. Association of *S. hominis* A9 bacteria abundance estimated CFU as measured by % *S. hominis* A9 positive colonies by PCR x CoNS CFU while CoNS CFU is above baseline density measured before application of ShA9 + 100 CFU/cm² on the lesional and non-lesional, separately, ventral arm skin of AD participants between the arm treated with *S. hominis* A9 and the contralateral arm treated with placebo, and independently, with the participant's face
2. The duration of survival, measured as the time needed for CoNS CFU to drop below baseline density measured before application of ShA9 + 100 CFU/cm² on the lesional ventral arm skin of AD participants negative for *S. aureus* (AD SA-)
3. The duration of survival, measured as the time needed for CoNS CFU to drop below baseline density measured before application of ShA9 + 100 CFU/cm² on the non-lesional ventral arm skin of AD participants negative for *S. aureus* (AD SA-)
4. Comparison of time needed for CoNS CFU to drop below baseline density measured before application of ShA9 + 100 CFU/cm² on the lesional and non-lesional, separately, ventral arm skin between AD participants positive (AD SA+) vs negative (AD SA-) for *S. aureus*
5. Comparison of time needed for CoNS CFU to drop below baseline density measured before application of ShA9 + 100 CFU/cm² on lesional vs non-lesional skin of AD participants positive (AD SA+) and negative (AD SA-) for *S. aureus*, separately
6. Comparison of the L-EASI score of the ventral arms at Day 0 vs the last in-clinic visit among AD SA+, and independently, among AD SA-
7. Comparison of the SCORAD score at Day 0 vs the last in-clinic visit among AD SA+, and independently, among AD SA-
8. Comparison of the local Pruritus NRS of the ventral arms at Day 0 vs the last in-clinic visit among AD SA+, and independently, among AD SA-

9. Comparison of the proportion of antibiotic-sensitive CoNS to penicillin G, tetracycline, and erythromycin isolated from skin swabs at baseline and after ShA9 treatment, at the last swab collection from lesional skin

13.3. Measures to Minimize Bias

Bias will be minimized by stratifying by arm-dominance and then randomizing active-dominant, placebo-non-dominant vs placebo-dominant, active-non-dominant, where active is considered *S. hominis* A9.

13.4. Analysis Plan

13.4.1 Analysis Populations

Safety Sample and modified ITT sample will include all participants who are enrolled and receive any amount of *S. hominis* A9. For analysis, *S. aureus* CFU results from swabs obtained prior to treatment application during the Treatment Visit will be used to define SA+ vs SA- status of participants.

13.4.2 Primary Analysis of Primary Endpoint

The primary endpoint for this pilot study is the time needed for CoNS CFU to drop below baseline density measured before application of ShA9 + 100 CFU/cm² (time-to-CoNS elimination) in AD participants positive for *S. aureus* colonization. Time-to-CoNS elimination is defined as the time from Day 0 to the first occurrence of a value below baseline density measured before application of ShA9 + 100 CFU/cm². The time to event for participants who did not reach CoNS CFU below baseline density measured before application of ShA9 + 100 CFU/cm² during the study will be right-censored.

Time-to-CoNS elimination distribution (i.e. overall survival) will be estimated using Kaplan Meier techniques. Median survival time along with 95% CI will be constructed based on a log-log transformed CI for the survivor function S(t). A graph of the Kaplan-Meier survival curve will be presented, and rates at fixed days will be derived (Therneau, et al., 2000). Furthermore, estimation of the hazard rate and 95% confidence interval will be produced using a parametric survival model.

13.4.3 Supportive Analyses of the Primary Endpoint

A nonlinear time-response regression analysis will be fitted between CoNS CFU/cm² and time, using either the two or three-parameter log-logistic model. Each of the models will be fitted to the data, and their fit compared using the Akaike information criteria (AIC), where the model with the lowest AIC will be the primary model for the derivation of the ED50 (or T50, time at which half of the maximum CoNS CFU/cm² is reached) (Ritz, et al., 2015).

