mouse skin, are more susceptible to killing by the human AMPs, such as cathelicidin and β -defensins -2 and -3 present on inflamed skin of patients with AD, and ShA9 increases survival upon deletion of its lantibiotics. To further test this hypothesis on human skin in the clinical setting, we measured abundance of ShA9 on the skin of participants from the Phase 1 trial under Protocol ADRN-08. We measured abundance of ShA9 on inflamed and non-inflamed skin. ShA9 abundance was measured by multiple approaches, including direct counting of total CoNS CFUs of live bacteria grown on selective agar plates, abundance of ShA9 DNA by qPCR, and measurement of mRNA by RT-qPCR for candidate ShA9 gene expression. Total CoNS CFUs were used as a surrogate measurement of live ShA9 CFU, since ShA9 is not specifically measurable by colony counting methods. However, since ShA9 is a type of CoNS, and the abundance of ShA9 applied greatly exceeded other CoNS recoverable from AD skin, this estimation was helpful to define live compared to dead bacteria. Furthermore, measurements by qPCR of ShA9 DNA and mRNA provide a more specific method to validate this assumption. On Day 0, an initial swab was collected one hour after application of ShA9 or vehicle. Both lesional and non-lesional skin showed a 3- to 4-log increase in live CoNS on the skin one hour after the first application of ShA9 but no change after application of the vehicle alone (Figure 1.4a). However, a difference in CoNS survival was observed between lesional and non-lesional sites at Days 4 and 7. At these time points, skin swabs were collected approximately four hours after the morning application. Swabs from lesional skin collected at these later times on Days 4 and 7 showed that live CoNS had decreased to a level similar to baseline, and no significant difference was detected in comparison to that from vehicle-treated subjects. This suggested the longer period between the morning application of ShA9 and the skin sampling resulted in a decrease in the live ShA9 recoverable by swab from lesional skin. In contrast, CoNS recovered from non-lesional skin was greater on both Day 4 and Day 7 on participants treated with ShA9 compared to vehicle (Figure 1.4a). These data support our preclinical observations that CoNS-AM+ bacteria survive less well in an inflamed skin environment that will have expression of human AMPs.

Figure 1.4a. CoNS-AM+ persist on non-lesional skin but not on inflamed skin of AD adult participants.

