# Compute the ED50 (or T50) from the selected model
if (best_model == "Two-parameter model") {
  ED50 <- ED(model_2par, 50)
} else {
  ED50 <- ED(model_3par, 50)
}
```

After conducting the model fits, we will evaluate the Akaike Information Criterion (AIC) for each model to compare their fit. The model yielding the lowest AIC will be selected as the primary model. From this primary model, we will determine the ED50 (or T50) - the time at which half of the maximum CoNS CFU/cm² is achieved. This approach follows the methodology outlined by Ritz et al., 2015. Adjustments or additional steps may be needed depending on the specifics of the data set and the research question at hand.

The supportive primary analysis will be conducted on the modified intent to treat sample and repeated on the per-protocol sample if it differs from the modified intent to treat sample.

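### The analysis labelled supportive of the primary endpoint reports only T50, a 0.3-log fall, which does not by itself determine the time to return to baseline + 100 CFU/cm²

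*Protocol*

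**What the plan says.** The primary endpoint (protocol 13.2.1) is "the time needed for the CoNS CFU to drop below baseline density measured before application of ShA9 + 100 CFU/cm²", on lesional skin of *S. aureus*-positive participants. Protocol 13.4.2 and SAP 7.3.1 take the event as the "first occurrence of a value below baseline density measured before application of ShA9 + 100 CFU/cm²". It is analysed by Kaplan-Meier, with a hazard rate from a parametric survival model.

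Protocol 13.4.3, headed as supportive of that endpoint, regresses CoNS CFU/cm² on time "using either the two or three-parameter log-logistic model", chooses between the two by AIC, and derives the "ED50 (or T50, time at which half of the maximum CoNS CFU/cm² is reached". SAP 7.3.3 again defines the result as "the time at which half of the maximum CoNS CFU/cm² is achieved". Its code extracts level 50 and no other, whichever model is chosen: see the line beginning "ED50 <- ED(model_3par, 50" and its two-parameter counterpart. The response in that code is untransformed CFU/cm². No other level, no slope and no fitted time to the primary threshold is planned. The only opening is the general sentence "Adjustments or additional steps may be needed depending on the specifics of the data set and the research question at hand".

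On the size of the rise, protocol 1.4 reports that both lesional and non-lesional skin in the earlier study "showed a 3- to 4-log increase in live CoNS on the skin one hour after the first application of ShA9".

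**The concern.** An analysis offered in support of a time-to-elimination endpoint should address the same event. T50 marks the first halving, while the event lies several logs further down. Two data sets with the same T50 can have very different elimination times, so agreement or disagreement between T50 and the Kaplan-Meier median says little about either.

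This matters because the protocol's stated aim is to learn the elimination rate and so inform dosing frequency (protocol 1.3 and 2.1). After Day 3 the swabs are seven days apart (Days 10, 17 and 24), so later Kaplan-Meier event times can fall only on widely spaced visits. A fitted curve could add a threshold-crossing time that uses all the swabs. As planned, it does not.

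**Working it through.** **The plan's own figure.** The documents give no figure for T50. The one design figure is the 95% CI width of 0.194 for a hazard of 0.15 with 9 events (protocol 13.7, SAP 11). The exact chi-square interval gives 0.15 × (31.526 − 8.231)/18 = 0.194, so it reproduces. It concerns the primary hazard estimate, which this point leaves untouched.

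**Step 1: size of the T50 fall.** log10(2) = 0.301.

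**Step 2: size of the fall to the event.** The fall is log10[peak/(baseline + 100)]. CoNS baseline is not given in the documents, so the values below are assumed.

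| Source of peak | Assumed baseline (CFU/cm²) | Fall needed (log10) |
|---|---|---|
| 3- to 4-log rise (earlier study) | 10 | 1.96 to 2.96 |
| same | 100 | 2.7 to 3.7 |
| same | 1,000 | 2.96 to 3.96 |
| Calculated applied density 1.27×10⁵ to 9.07×10⁶ (protocol 6.1.1.2.1) | 0 | 3.1 to 5.0 |
| same | 1,000 | 2.1 to 3.9 |
| Bottom of acceptable dosage range, 2×10³ | 0 to 100 | 1.3 to 1.0 |

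So 2 to 4 logs is a fair general description, with about 1.3 logs or less at the lowest acceptable dose.

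**Step 3: what T50 implies for that fall.** The three-parameter log-logistic has lower limit zero: f(t) = d/[1 + (t/T50)^b]. Solving for a fall of k logs gives t = T50 × (10^k − 1)^(1/b). The slope b is free and no value is given, so a range is assumed. With T50 = 1 h (also assumed):

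| b | 2-log fall | 3-log fall | 4-log fall |
|---|---|---|---|
| 1 | 4.1 days | 41.6 days | 416.6 days |
| 1.5 | 21.4 h | 4.2 days | 19.3 days |
| 2 | 9.9 h | 31.6 h | 4.2 days |
| 3 | 4.6 h | 10.0 h | 21.5 h |
| 4 | 3.2 h | 5.6 h | 10.0 h |

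Inverting, b = ln(10^k − 1)/ln(t/T50). For a 3-log fall, elimination at 6 h needs b = 3.85 and elimination at Day 24 (576 h) needs b = 1.09. For 4 logs the values are 5.14 and 1.45. A modest range of slopes therefore covers the whole follow-up at one T50.

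**Step 4: can the crossing time be read off the planned fit?** Not usefully. A rough simulation used 13 participants, the protocol's swab times and noise of 0.5 log10. The curve was baseline + 10⁶/[1 + (t/1 h)²], with baselines around 10³ CFU/cm². All values except the swab times and the 13 participants are assumptions. The true crossing of baseline + 100 is at (10⁶/100 − 1)^(1/2) = 100 h. With each participant's baseline as lower limit, the 5th to 95th percentiles of the estimate were:

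- raw CFU/cm² scale, as in the SAP code: 3 to 9,578 h (the upper figure is unstable; another run gave 4,330 h);
- log10 scale: 61 to 196 h.

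On the raw scale the few highest early counts dominate, and the values near the threshold carry almost no weight. SAP section 3 already treats CoNS CFU as lognormal, so the log scale is also the consistent choice.

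**The case against.** The strongest reply is that nothing important is lost. Elimination time is already estimated directly by the Kaplan-Meier median, the rates at fixed days and the hazard; SAP 7.2 adds individual trajectories; both documents define T50 plainly; and a half-time is a legitimate kinetic summary when five swabs fall in the first 6 hours. This stands as to consequence, and it is why T50 should be kept. It does not make T50 a check on the primary endpoint.

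A second reply is that b is estimated together with T50, so the fitted model does imply an elimination time. That is correct: the hours-to-weeks spread describes T50 read alone, not the fitted curve. But the plan does not report b or that time, and step 4 shows that the raw-scale fit would give it with almost no precision. Under simple first-order decay T50 would fix elimination at 10.0 to 13.3 × T50 for 3 to 4 logs, but that is not the plan's model.

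A reader might go further and infer that T50 will fall within minutes of application, because lesional CoNS in the earlier study was near baseline about four hours after a dose. The documents do not support this. That observation comes from Days 4 and 7 of repeated dosing in a different vehicle, and the inference needs log-linear decay. It also sits badly with the planning hazards of 0.09 and 0.15 (per day, as the 11-day follow-up implies), whose exponential medians are ln 2/0.09 = 7.7 and ln 2/0.15 = 4.6 days. Under the same log-linear assumption those give T50 of 4.6 × 24/13.3 = 8.3 h to 7.7 × 24/10.0 = 18.5 h. Nor can T50 be dismissed as lying within swab noise: the documents give no swab-to-swab SD, and T50 would be estimated from about 130 observations (13 participants × 10 swab times), not from one pair.

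**Conclusion.** The point holds for the supportive analysis. T50 is a 0.301-log fall, and the primary event is typically 2 to 4 logs down. In the planned model T50 alone leaves the time to a 3-log fall anywhere from 5.6 h (b = 4) to 41.6 days (b = 1) when T50 is 1 h.

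This rests on assumed values for b, baseline and T50, and on a 3- to 4-log rise carried over from a study with another formulation. The conclusion survives a 2-log fall (3.2 h to 4.1 days) and weakens at the lowest acceptable dose, where about 1.3 logs or less is needed.

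It would be wrong to infer that the primary result is compromised. The Kaplan-Meier analysis does not use T50, and no test or decision rests on it. The consequence is modest: a supportive analysis that cannot confirm or challenge what it is meant to support.

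**What to change.** In protocol 13.4.3 and SAP 7.3.3:

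1. Keep T50, labelled as a measure of early loss only.
2. Make the main supportive result the model-based time at which the curve reaches baseline + 100 CFU/cm², with its 95% CI. Report T90 and T99 from the same fit.
3. Fit log10 CoNS CFU/cm², with the lower limit set to each participant's Day 0 pre-application density instead of zero. State whether T50, T90 and T99 refer to the excess over that limit.
4. State the baseline at which a pooled curve's crossing is read, for example the geometric mean, because the threshold differs between participants.
5. Do not derive the crossing time from the raw-scale fit.

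The cost is SAP wording and a little more analysis code, with no new data. The CI for the crossing time will be wider than that for T50, and it should be shown.
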